4.2.2 Restrictions

4.2.2.1 Restrictions regarding concomitant treatment

The aim of the study is to investigate the efficacy and safety of nintedanib in patients whose progressive lung disease is the main contributor to morbidity.

Treatment of ILD

Immunomodulatory medications i.e. Azathioprine, cyclosporine, tacrolimus, Rituximab, Cyclophosphamide, mycophenolate mofetil, OCS have been utilized in the clinical practice for the treatment of ILD although their benefit-risk profiles in ILD have not been established and they are not approved for the treatment of ILD in most countries. In order to avoid the potential impact of these drugs on the assessment of the efficacy and safety of nintedanib in PF-ILD, their use will not be allowed at randomization and during the first six months of the treatment period.

Patients who receive any of these medications for the treatment of their ILD will have to discontinue these drugs prior to randomization. As the protocol requires that eligible patients progress despite treatment with these medications (i.e. do not or no longer benefit from these drugs), prohibition of these medications is considered justified. In case of acute worsening of PF-ILD during the treatment period, the use of any of these drugs after six months of study treatment will be allowed if judged necessary by the investigator.

Treatment of the underlying diseases associated with ILD

The largest group of patients with PF-ILD that has an underlying disease associated with ILD is the group of patients with CTD. Eligible patients with underlying CTD should have *stable* CTD defined as no initiation or withdrawal of therapy for CTD within six weeks prior to screening. In addition, investigators are encouraged to maintain the baseline treatment of CTD during the entire study unless change is medically indicated.

The majority of the eligible patients with CTD is expected to have RA and to be receiving disease-modifying anti-rheumatic drug (DMARD) e.g. methotrexate or TNF inhibitors. All approved RA/CTD medications are allowed at stable doses at Baseline (Visit 2) and during the study with the exceptions of the following, less frequently used medications:

Azathioprine, cyclosporine, tacrolimus, high dose steroids, and Rituximab. The use of these medications will not be allowed in this study. In addition, the following drugs used off-label for the treatment of RA/CTD will not be allowed throughout the study: Cyclophosphamide and MMF.

The rationale for these limitations is that, as described above, these drugs have also been utilized in the clinical practice for the treatment of ILD. In order to avoid the potential impact of these drugs on the assessment of the efficacy and safety of nintedanib in PF-ILD, their use will not be allowed.

Patients whose RA/CTD is well managed by these medications should not be considered for participation in the current study. In case a change in the RA/CTD treatment to another non-restricted medication is indicated, the patient's disease has to be stable (i.e. no initiation of new therapy or withdrawal of therapy for CTD within 6 weeks prior to Visit 1) before entering in the current trial.

Table 4.2.2.1: 1 Medication restrictions

Restricted medications: Azathioprine, cyclosporine, tacrolimus, Rituximab, Cyclophosphamide, mycophenolate mofetil, OCS >20mg/day, investigational drugs		
	For ILD	For CTD
Baseline	Not allowed at V2*	Not allowed
Within first 6 months of study treatment	Not allowed	Not allowed
After 6 months of study treatment	Allowed in case of significant deterioration [#]	Allowed case of significant deterioration [#]
After EOT	Allowed	Allowed

* Wash-out periods to be observed as described in [Table 4.2.2.1: 2](#) below

[#] All can be used in case of clinically significant deterioration of PF-ILD or worsening CTD at the discretion of the Investigator, except for investigational drugs. Introduction of new therapy for CTD should be minimized.

Table 4.2.2.1: 2 Wash-out schedule. Wash-out rules apply only for medications used for ILD treatment.

Medication	Wash-out period
Azathioprine Cyclosporine Tacrolimus Mycophenolate mofetil OCS >20mg/day	4 weeks prior to Visit 2
Rituximab	6 months prior to Visit 2
Cyclophosphamide	8 weeks prior to Visit 2
Investigational drug(s)	4 weeks or 6 half-lives (whichever is longer) prior to Visit 1

In case of clinically significant deterioration, initiation of additional therapy for ILD i.e. on top of the study medication is allowed after completion of the 6-month study visit (Visit 7) as described in [Table 4.2.2.1:1](#), as determined by the Investigator. For example, introduction of additional therapy may be considered if the patient experiences $\geq 10\%$ relative decline in FVC% pred from baseline that is not attributed to a reversible process (i.e. respiratory infection). Detailed (S)AE information following such events should be recorded in the eCRF. Please also refer to cautionary notes ([Section 4.2.2.2](#)).

Prohibited medications

As detailed in the exclusion criteria, patients receiving *pirfenidone, nintedanib, full dose therapeutic anticoagulation or high dose antiplatelet therapy* (e.g. acetyl salicylic acid >325 mg/day, or clopidogrel >75 mg/day, or equivalent doses of other antiplatelet therapy) are not eligible for participation in the study.

The use of pirfenidone and nintedanib are prohibited throughout the study, including the Follow-up period.

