3.3.2 Inclusion criteria

1. Written Informed Consent consistent with ICH-GCP and local laws signed prior to entry into the study (and prior to any study procedure including shipment of HRCT to reviewer).
2. Male or female patients aged ≥ 18 years at Visit 1.
3. Patients with physician diagnosed ILD who fulfil at least one of the following criteria for PF-ILD within 24 months of screening visit (Visit 1) despite treatment with unapproved medications used in clinical practice to treat ILD, as assessed by the investigator (refer to [Exclusion Criteria](#)):
 - a. Clinically significant decline in FVC % pred based on a relative decline of $\geq 10\%$
 - b. Marginal decline in FVC % pred based on a relative decline of $\geq 5\%-<10\%$ combined with worsening of respiratory symptoms
 - c. Marginal decline in FVC % pred based on a relative decline of $\geq 5\%-<10\%$ combined with increasing extent of fibrotic changes on chest imaging
 - d. Worsening of respiratory symptoms as well as increasing extent of fibrotic changes on chest imaging

[Note: Changes attributable to comorbidities e.g. infection, heart failure must be excluded. Unapproved medications used in the clinical practice to treat ILD include but are not limited to corticosteroid, azathioprine, mycophenolate mofetil (MMF), n-acetylcysteine (NAC), rituximab, cyclophosphamide, cyclosporine, tacrolimus].
4. Fibrosing lung disease on HRCT, defined as reticular abnormality with traction bronchiectasis with or without honeycombing, with disease extent of $>10\%$, performed within 12 months of Visit 1 as confirmed by central readers.
5. For patients with underlying CTD: stable CTD as defined by no initiation of new therapy or withdrawal of therapy for CTD within 6 weeks prior to Visit 1.
6. DLCO corrected for Haemoglobin (Hb) [visit 1] $\geq 30\%$ and $<80\%$ predicted of normal at Visit 2 (refer to [Appendix 10.1](#)).
7. FVC $\geq 45\%$ predicted at Visit 2 (refer to Appendix 10.1).

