3.3.3 Exclusion criteria

1. AST, ALT $> 1.5 \times$ ULN at Visit 1
2. Bilirubin $> 1.5 \times$ ULN at Visit 1
3. Creatinine clearance <30 mL/min calculated by Cockcroft–Gault formula at Visit 1 (refer to [Appendix 10.2](#)).

[Note: Laboratory parameters from Visit 1 have to satisfy the laboratory threshold values as shown above. Visit 2 laboratory results will be available only after randomization. In case at Visit 2 the results do no longer satisfy the entry criteria, the Investigator has to decide whether it is justified that the patient remains on study drug. The justification for decision needs to be documented. Laboratory parameters that are

found to be abnormal at Visit 1 are allowed to be re-tested (once) if it is thought to be a measurement error (i.e. there was no abnormal result of this test in the recent history of the patient and there is no related clinical sign) or the result of a temporary and reversible medical condition, once that condition is resolved].

4. Patients with underlying chronic liver disease (Child Pugh A, B or C hepatic impairment).
5. Previous treatment with nintedanib or pirfenidone.
6. Other investigational therapy received within 1 month or 6 half-lives (whichever was greater) prior to screening visit (Visit 1).
7. Use of any of the following medications for the treatment of ILD: azathioprine (AZA), cyclosporine, MMF, tacrolimus, oral corticosteroids (OCS) >20mg/day and the combination of OCS+AZA+NAC within 4 weeks of Visit 2, cyclophosphamide within 8 weeks of Visit 2, rituximab within 6 months of Visit 2.
Note: Patients whose RA/CTD is managed by these medications should not be considered for participation in the current study unless change in RA/CTD medication is medically indicated (refer to [Inclusion Criterion #5](#))
8. Diagnosis of IPF based on ATS/ERS/JRS/ALAT 2011 Guidelines ([P11-07084](#)).
9. Significant Pulmonary Arterial Hypertension (PAH) defined by any of the following:
 - a. Previous clinical or echocardiographic evidence of significant right heart failure
 - b. History of right heart catheterization showing a cardiac index ≤ 2 l/min/m²
 - c. PAH requiring parenteral therapy with epoprostenol/treprostilin
10. Primary obstructive airway physiology (pre-bronchodilator FEV1/FVC < 0.7 at Visit 1).
11. In the opinion of the Investigator, other clinically significant pulmonary abnormalities.
12. Major extrapulmonary physiological restriction (e.g. chest wall abnormality, large pleural effusion)

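### Protocol 4.2.2.1 bars oral corticosteroids for ILD with no dose limit, while exclusion criterion 7, both 4.2.2.1 tables and SAP deviations A2.3 and D1 restrict them only above 20 mg/day

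*Protocol*

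**What the plan says.** The Treatment of ILD text in Protocol 4.2.2.1 begins with a drug list: "Immunomodulatory medications i.e. Azathioprine, cyclosporine, tacrolimus, Rituximab, Cyclophosphamide, mycophenolate mofetil, OCS have been utilized in the clinical practice for the treatment of ILD". OCS carries no dose. Two instructions follow for the whole list. One says that "their use will not be allowed at randomization and during the first six months of the treatment period". The other says: "Patients who receive any of these medications for the treatment of their ILD will have to discontinue these drugs prior to randomization".

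Elsewhere the restriction has a dose:

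- Exclusion criterion 7 (Protocol 3.3.3) names "oral corticosteroids (OCS) >20mg/day and the combination of OCS+AZA+NAC within 4 weeks of Visit 2".
- Table 4.2.2.1: 1, the list of restricted medications, includes "mycophenolate mofetil, OCS >20mg/day, investigational drugs".
- Table 4.2.2.1: 2, the wash-out schedule, has one row for "Azathioprine Cyclosporine Tacrolimus Mycophenolate mofetil OCS >20mg/day" and none for lower OCS doses.
- In SAP Table 6.2: 1, deviations A2.3 (prior therapy) and D1 (concomitant therapy) both use more than 20 mg/day.

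The CTD paragraph of the same protocol section lists "Azathioprine, cyclosporine, tacrolimus, high dose steroids, and Rituximab", so it too limits the steroid restriction to high doses.

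SAP 7.2.2 plans an output of on-treatment restricted therapies. It refers to Section 9.8 for the drug codes and to Protocol 4.2.2 for the definitions. The OCS row of SAP Table 9.8: 1 is marked restricted and gives a code without a dose.

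**The concern.** A patient taking 20 mg/day or less of OCS for ILD is treated differently depending on which part of the protocol the site reads. Under the Treatment of ILD text the drug must be stopped before randomisation and not started in the first six months. Under criterion 7 and the two tables it may continue, with no wash-out.

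The situation is foreseeable. The note to inclusion criterion 3 reads "Unapproved medications used in the clinical practice to treat ILD include but are not limited to corticosteroid", and corticosteroid is the first of eight drugs it names. What is at stake is mainly patient care and uniform conduct across sites: a permitted steroid could be withdrawn before baseline, or withheld later, because of a wording slip. On the reporting side, the restricted-therapy output could attach the restricted label to use that the protocol allows.

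**Working it through.** There is no arithmetic to do. The seven statements are set side by side.

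| Place | What it governs | OCS limit |
|---|---|---|
| Protocol 4.2.2.1, Treatment of ILD text | Stopping before randomisation; use at randomisation and in the first six months | None stated |
| Protocol 3.3.3, exclusion criterion 7 | Eligibility | >20 mg/day, plus the OCS+AZA+NAC combination |
| Protocol Table 4.2.2.1: 1 | Restrictions at baseline and on treatment | >20 mg/day |
| Protocol Table 4.2.2.1: 2 | Wash-out before Visit 2 | >20 mg/day |
| SAP Table 6.2: 1, A2.3 | Important deviation, prior therapy | >20 mg/day, plus the OCS+AZA+NAC combination |
| SAP Table 6.2: 1, D1 | Important deviation, concomitant therapy | >20 mg/day |
| SAP Table 9.8: 1 | Drug codes for restricted therapies | None stated |

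Five statements carry the limit and two do not.

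**Which rule is intended.** If the ban had no dose limit, the wash-out table would need an entry for lower doses. It has none. Together with the high-dose wording for CTD, this makes >20 mg/day almost certainly the intended rule and the missing dose a drafting omission.

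**Patient on low-dose OCS for ILD at screening (no AZA or NAC).** By criterion 7 the patient is eligible. By the wash-out table nothing has to be stopped. A2.3 and D1 flag nothing. By the Treatment of ILD text the drug must be stopped.

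**Low-dose OCS started in the first six months.** Table 4.2.2.1: 1 does not restrict it; the text does. The exception is an acute exacerbation, where Protocol 4.2.1.3 allows any treatment the investigator thinks adequate. After six months the text itself allows the listed drugs for acute worsening, so the conflict lies mainly at baseline and in the first six months.

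**SAP output.** SAP 7.2.2 defines on-treatment therapies as those started from first to last trial drug intake. Low-dose OCS continued from baseline is therefore a baseline therapy and is not in this output. Only new starts of 20 mg/day or less could be labelled restricted, and only if no dose filter is applied.

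**Effect on the confirmatory analysis.** SAP 7.4.1 uses the treated set with data collected after discontinuation. D1 excludes nobody. SAP 7.2 makes the concomitant-medication section descriptive only. No primary-analysis, alpha or power figure depends on the OCS wording.

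**The case against.** The best defence is that the ILD sentence is rationale and the operative rules come straight after it. Table 4.2.2.1: 1 is the list labelled as restricted medications, criterion 7 sets eligibility, and Table 4.2.2.1: 2 sets wash-out; all three carry the dose. No document shows a site acting on the unqualified text. This stands as a reason to rate the point minor. It does not remove the point, because the two sentences after the drug list are instructions, and nothing in 4.2.2.1 says that the tables override the text.

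A reader might go further and infer that low-dose OCS would force permanent discontinuation of trial drug, since Protocol 3.3.5.1 requires this for restricted concomitant treatment as Section 4.2.2 defines it. The documents do not support that as a likely outcome: the only list in Section 4.2.2 labelled as restricted medications has the >20 mg/day limit.

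A reader might also infer that the SAP's restricted-therapy output would wrongly contradict D1. That does not follow either. The output is not a count of violations. It includes restricted drugs that are permitted after six months for deterioration, whereas D1 depends on manual review for documented exacerbation or worsening. The two would differ even with a dose filter. In addition, SAP 7.2.2 leaves the definition to Protocol 4.2.2, so Table 9.8: 1 can fairly be read as a coding look-up. What remains is that its OCS row, applied as written, has no dose.

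**Conclusion.** The inconsistency is real and minor. The Treatment of ILD text states a wider rule than the protocol's own eligibility criterion, restriction table and wash-out table, and wider than both SAP deviations. Taken literally, it tells sites to withdraw or withhold OCS of 20 mg/day or less that is otherwise allowed. The gap in SAP Table 9.8: 1 is smaller and touches one descriptive output, for newly started OCS only.

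The documents do not say how many patients took 20 mg/day or less, so the number affected is unknown and may be zero. The conclusion rests on reading >20 mg/day as the intended limit, for the reasons given above.

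**What to change.** Insert >20 mg/day after OCS in the Treatment of ILD text of Protocol 4.2.2.1. Add a >20 mg/day condition, or a footnote to that effect, to the OCS row of SAP Table 9.8: 1. Leave the reference in 3.3.5.1 to Section 4.2.2 as it is, because that section also holds the ban on pirfenidone and non-trial nintedanib, which Table 4.2.2.1: 1 does not name.

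Send sites a short clarification only if patients are still in screening or in their first six months of treatment. The documents do not give recruitment status, although the final SAP of 14 December 2018 already reports patients randomised by mistake, which suggests that enrolment was well advanced. The cost is a few words in one protocol paragraph and one SAP condition or footnote, plus the clarification if it is needed. Data collection and the primary analysis do not change.

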4.2.1.3 Management of acute ILD exacerbations

In case of acute ILD exacerbation (see [Section 5.2.4](#)), all treatment options considered adequate by the Investigator are allowed. The patient may interrupt study treatment for up to 8 weeks, if necessary (e.g. if short-term full anticoagulation is performed).

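### Protocol 4.2.2.1 contradicts itself on drugs for connective tissue disease (CTD): the text bans seven without time limit, while Table 4.2.2.1: 1 allows them after 6 months on deterioration and unconditionally after end of treatment (EOT)

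*Protocol*

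**What the plan says.** Protocol 4.2.2.1 deals with CTD treatment twice.

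**In the text.** The scope is set first: "All approved RA/CTD medications are allowed at stable doses at Baseline (Visit 2) and during the study with the exceptions of the following". Five items are then excepted (azathioprine, cyclosporine, tacrolimus, high dose steroids, rituximab), followed by "The use of these medications will not be allowed in this study". Two further drugs, used off-label, "will not be allowed throughout the study: Cyclophosphamide and MMF". The rationale paragraph repeats the ban, again with no period attached: to protect the assessment of "nintedanib in PF-ILD, their use will not be allowed".

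**In the table.** Table 4.2.2.1: 1 lists the same drugs as restricted, giving steroids as OCS >20mg/day and adding investigational drugs. Its CTD column bars them at baseline and in the first 6 months. After 6 months the entry is "Allowed case of significant deterioration". After EOT they are allowed with no condition. Footnote # says "All can be used in case of clinically significant deterioration of PF-ILD or worsening CTD at the discretion of the Investigator", with investigational drugs as the only exclusion, and asks that new CTD therapy be kept to a minimum.

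**Elsewhere.** The ILD paragraph of the same section limits its own ban to the first six months and then says that "the use of any of these drugs after six months of study treatment will be allowed if judged necessary by the investigator". Protocol 3.3.5.1 makes restricted concomitant treatment, as defined in Section 4.2.2, a reason for permanent discontinuation of trial drug. SAP Table 6.2: 1, code D1(b), flags use after 6 months only where ILD or CTD has not significantly deteriorated.

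**The concern.** The two rules give opposite answers for the same drugs, the same indication and the same period. A patient whose CTD flares after Visit 7 may receive rituximab under the table but not under the text. Because the stopping rule in Protocol 3.3.5.1 points to the section that conflicts, the disagreement can reach trial drug as well as CTD care.

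Three things are at stake: the care of CTD patients who worsen, uniform handling across sites, and those analyses that depend on when trial drug was stopped. Protocol 4.2.2.1 describes CTD as the largest group with an underlying disease associated with ILD. Part B continues blinded treatment beyond week 52, so the question does not end with the primary analysis period.

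**Working it through.** There is no planned figure to reproduce. The check compares the two rules drug by drug and period by period.

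**Drugs.** The text names 5 + 2 = 7 items. Six match the table by name. The seventh, high dose steroids, matches only if it is read as OCS >20mg/day. That reading is reasonable, since exclusion criterion 7 uses the same threshold, but the CTD text itself gives no dose.

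**Periods, for CTD use:**

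| Period | Text | Table 4.2.2.1: 1 and footnote # | Agree? |
|---|---|---|---|
| Baseline | Not allowed | Not allowed | Yes |
| First 6 months of study treatment | Not allowed | Not allowed | Yes |
| After 6 months | Not allowed | Allowed on significant deterioration | No |
| After EOT | Not allowed | Allowed | No |

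The last row matters because patients who stop trial drug early are asked to stay in the study and attend the remaining visits (Protocol 3.1, 3.3.5.1, 6.2.3). A ban covering the study therefore still applies to them on its face.

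**Can the text be read as a general rule with the table as its exception?**
- For cyclophosphamide and MMF, no. A ban for the entire study leaves no period for an exception.
- For the other five the reading is strained. The lead-in covers baseline and the study itself, so this is not an entry-only rule. The neighbouring ILD paragraph shows how the protocol words a ban with a 6-month limit and a later exception; the CTD paragraph has neither.
- No other passage supplies the exception. Protocol 2.3, the Part B justification in 3.2, and the paragraph after the wash-out table in 4.2.2.1 concern therapy for ILD. The placebo-control discussion in 3.2 speaks of worsening disease without mentioning CTD.

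**Is the CTD column a slip?** Unlikely. Footnote # names worsening CTD explicitly, and SAP D1(b) applies the same rule. The text is the part to correct.

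**What could change in the analyses if a patient is stopped because of the text?**
- Primary analysis (SAP 7.4.1): all FVC up to day 373 is used, including values after discontinuation, so the measurements are kept.
- Missing-data patterns (SAP 7.4.2.1.2): a patient with a week 52 FVC moves from pattern 1 to pattern 2, the pattern on which sensitivity analyses 1 and 2 draw.
- On-treatment analysis (SAP 7.4.2.1.1, Table 6.1.1: 1): FVC after last drug intake is dropped. Of the seven scheduled post-baseline values (weeks 2, 4, 6, 12, 24, 36, 52), only those after Visit 7 at week 24 can be lost, so at most two.
- Deviation D1: for CTD use, D1(a) and D1(b) already match the table, so the classification does not change.

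**The case against.** The best defence is that the intended rule can be recovered. The table, its footnote and SAP D1(b) agree, and the text tells investigators to keep baseline CTD therapy unless a change is medically indicated. Protocol 3.3.5.1 speaks of restricted treatment, and the only list in Section 4.2.2 under that name is Table 4.2.2.1: 1, which carries the allowance. An investigator who looks there would find the drug permitted. Permanent discontinuation follows only if the table is passed over.

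Most of this stands, and it limits the consequence. A reader might infer that investigators would refuse the drug or would stop trial drug. The documents support only that they could. A reader might also infer that the conflict biases the primary result or distorts the deviation counts. SAP 7.4.1 keeps FVC after discontinuation, and D1 follows the table, so neither inference is supported.

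It does not remove the conflict. Sites work from the protocol, and the SAP does not correct what they read. A ban stated for the entire study and an allowance after 6 months cannot both be followed.

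**Conclusion.** Protocol 4.2.2.1 is internally inconsistent on CTD treatment after 6 months and after EOT, and the text is wrong as written. The conflict bears on patient care and, through 3.3.5.1, on stopping trial drug. It should be corrected, but it does not threaten the primary result.

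The number of patients affected cannot be derived: the documents give neither an expected number of CTD patients nor a rate of CTD worsening after Visit 7. The text describes the approved drugs on its list as less frequently used for CTD, which suggests that few patients are involved without giving a count. It is tempting to measure the problem by the slope information lost when a patient stops after Visit 7. That would need a within-patient residual SD that the documents do not give, and it would describe any stop at that time, whatever the reason. It is not a measure of this inconsistency.

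The conclusion rests on reading high dose steroids as OCS >20mg/day for one of the seven items. For the other six it needs no assumption.

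**What to change.** Replace the unlimited CTD bans in the text of Protocol 4.2.2.1, including the repeat in the rationale paragraph, with:

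*Azathioprine, cyclosporine, tacrolimus, rituximab, cyclophosphamide, MMF and OCS >20mg/day are not allowed for CTD at baseline or in the first 6 months of study treatment. After 6 months of study treatment they are allowed, on top of trial drug, in case of significant deterioration, and after EOT they are allowed, as in Table 4.2.2.1: 1 and footnote #.*

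This covers all four rows of the table and gives the steroid rule a dose. Use permitted by the table is then not a reason to stop trial drug under Protocol 3.3.5.1, whose reference to Section 4.2.2 can stay. If that rule is also clarified, it should point to Sections 4.2.1.3 and 4.2.2 and not to the table alone. In an acute ILD exacerbation "all treatment options considered adequate by the Investigator are allowed", and the bans on pirfenidone and non-study nintedanib sit in 4.2.2 outside the table.

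Cost: one wording change, which needs ethics committee and authority approval as an amendment (Protocol 8.1) and can be bundled with another. There is no change to the SAP, data collection or sample size.
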